4.5. Heterogeneity of effects and pre-specified subgroup analyses

With the small but clinically meaningful effect size we seek to detect, we have insufficient power to evaluate the EDTR rate in all subgroups of interest. Accordingly, subgroup analyses to assess for heterogeneity in treatment effects will be noted as exploratory and limited to pre-specified salient domains. Of greatest interest are:

1. Cohort (MO or Surg);
2. Region of Site (Northern, Southern, or Metropolitan)
3. Age [year] (<70 or >=70);
4. Sex (Male or Female);
5. Race (White/Non-Hispanic or Others);
6. Cancer type (GI, Gyn, or Thoracic); and
7. Rurality inferred from population density in the patient's zip code of residence (large metro, small metro, suburban, or rural).

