- Secondary: Sites will be included as random-effects with a small sample adjustment (the Kenward-Roger method).^{11,12}
- Subjects
 - We will potentially have more than one data point from one subject in this study.
 - To take account of within-subject correlation, subjects will be included as random effects.
 - The primary analysis will consider random intercepts only.
- Variables to be included the GLMM
 - **Table 8** lists the variables selected based on the study design (Category A) and clinical importance (Category B and C).
 - The primary analysis includes the variables in Category A and B.
 - As a secondary analysis, we will perform the same analysis including Category A, B and C.

Table 8: Variables that will or may be included in the generalized linear mixed-effects model for the primary analysis

Variable	Category A	Category B	Category C
Intervention indicator: (eSyM+ vs. eSyM-)	X		
Cohort (MO vs. Surgery)	X		
Calendar Time (Secular trends) [continuous with natural cubic spline]	X		
Site (Treating Facility) (DFCI, MMC, DHMC, LCI, BAPT, WVU) [as fixed effects]	X		
Interaction between Cohort (MO vs. Surgery) and Calendar Time (Secular trends)	X		
Interaction between Cohort (MO vs. Surgery) Site (Treating Facility) (DFCI, MMC, DHMC, LCI, BAPT, WVU) [as fixed effects]	X		
Subjects [as random effects (random intercepts only)]	X		
Goal of Chemotherapy (MO with curative goal, MO with palliative goal, Others)		X	
Age (years) (fractional polynomials)		X	
Sex (male vs. female)		X	
Race/Ethnicity (white/non-Hispanic, black/non-Hispanic, Hispanic, Other/Unknown)		X	
Rurality based on zip code (large metro, small metro, suburban, rural)		X	
Cancer/procedure type (GI, Gyn, Thoracic)		X	
Employment (Employed, Disabled, Retired, Other)			X
Marital status (Married vs. Not married)			X
Insurance type (Medicare only, Medicare and Medicaid, Medicaid only, Private, Other)			X
Socio-economic status (quintiles by the zip code-based poverty level)			X
Co-morbidity (Charlson comorbidity index from encounter diagnoses in the 12 months before the first eligibility date) (0, 1, 2+)			X

- Time decay of the intervention effect

- As a sensitivity analysis, we will include the interaction between the intervention and time from the rollout of the intervention condition at the treating site to the time of the trigger event, where we treat the time as a categorical variable in the model.

Considerations on the potential informative censoring

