4.6. Sensitivity analyses

Change in eSyM recall period:

During the study, there was a minor update to the eSyM symptom questionnaire. eSyM originally collected symptom information with a 7-day recall period, but a mid-study update altered this to a 24-hour recall period. Using eSyM+ data only, we will summarize frequencies of severe symptoms reported before the update and after the update. For the evaluation of eSyM intervention, we will not distinguish eSyM intervention before and after the update in the primary analysis. As sensitivity analyses, we will assess the impact of this update on each outcome.

- Sensitivity Analysis 1: We will run the same analysis as the primary analysis, excluding the eSyM+ episodes with a 7-day recall period.
- Sensitivity Analysis 2: We will modify the GLMM model used for the primary analysis. The intervention group variable will be a categorical variable with three levels – control, eSyM+ with 7-day recall, and eSyM+ with 24-hour recall. We will test if there is any difference between the 7-day and 24-hour recall.

Missing data:

Given the short 30-day interval for the Aim 2a primary endpoint and our pragmatic outcome, we expect the dropout fraction and missing data at Day 30 to be negligible. Subjects with no hospital encounters by Day 30 will be included in the analysis as having had no EDTR.

Regarding missing covariates, the primary analysis will be based on the following data handling.

- 1) Race/Ethnicity: Subjects with missing race/ethnicity are categorized as “Other/Unknown” and included in the analysis.
- 2) Employment: Subjects with missing employment information are categorized as “Other/Unknown” and included in the analysis.
- 3) Insurance type: Subjects with missing insurance type are categorized as “Other/Unknown” and included in the analysis.
- 4) Rurality: Subjects with missing rurality will be excluded from the analysis.
- 5) Socio-economic status: Subjects with missing socio-economic status are classified as “poverty level 2” and included in the analysis.

Note that the preliminary data check found that the other covariates do not have missing values.

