In secondary analysis, we will perform multiple imputations with chained equations for Rurality. Specifically, the imputation models will include the primary outcome (EDTR Day 30), all variables used for the primary analysis (Category A and B), and the variables in C (as auxiliary variables) listed in Table 8. The number of complete datasets we generate will basically the same as the percentage of the fraction of missing. For example, if the missing fraction is 10%, we will generate 10 complete datasets. However, if the fraction of missing is less than 5%, we will generate 5 complete datasets. We will analyze each complete data and obtain the point estimate and the standard error for the intervention effects. We will then pool the results from the multiple complete datasets using Rubin’s method.¹³

Analysis with data from the first episode:

In the primary analysis, all episodes in the analyses except for eSyM- episodes contaminated with the eSyM intervention will be included. We will perform sensitivity analyses using only the first episode from each patient. In these sensitivity analyses, each patient will serve only one data point in the analysis.

Modeling for the COVID19

As a sensitivity analysis, we will include the site-specific COVID19 prevalence as a time-varying covariate in the model.

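### As written, patients with missing race are pooled with recorded minority patients in the exploratory race subgroup, which can dilute the contrast by an amount the documents do not fix

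*SAP*

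**What the plan says.** Three places in the SAP bear on this.

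- Section 4.5, item 5, defines the subgroup with two levels: "Race (White/Non-Hispanic or Others". The section labels the whole family as exploratory ("subgroup analyses to assess for heterogeneity in treatment effects will be noted as exploratory and limited to pre-specified salient domains") and concedes that "we have insufficient power to evaluate the EDTR rate in all subgroups of interest".
- Section 4.6, under missing data, opens with "Regarding missing covariates, the primary analysis will be based on the following data handling". Its first rule is that "Subjects with missing race/ethnicity are categorized as" the combined *Other/Unknown* level, and these patients stay in the analysis.
- Table 8 in section 4.4 carries the same coding into the outcome model: "Race/Ethnicity (white/non-Hispanic, black/non-Hispanic, Hispanic, Other/Unknown". There is no level for unknown race alone. Table 7, for the propensity models, has the same four levels.

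Rurality is handled differently. Section 4.6 drops patients with missing rurality from the primary analysis and then adds imputation: "In secondary analysis, we will perform multiple imputations with chained equations for Rurality". No imputation is planned for race. The June 2024 addendum, which moves the primary analysis to first episodes, leaves all of this unchanged.

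**The concern.** A combined *Other/Unknown* level does little harm as an adjustment covariate, because it only absorbs some baseline variation. A subgroup is different: its label says whose treatment effect is being estimated. If missing race is folded into *Others*, that row is no longer an estimate for patients recorded as Black, Hispanic or of another race. It is a mixture of them with patients whose race nobody wrote down.

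The quantity at stake is the White versus *Others* difference in the eSyM effect on emergency department treat-and-release visits. Any White, non-Hispanic patients hidden among the unknowns pull the *Others* estimate toward the White estimate, so a real difference looks smaller. Race is among the domains that section 4.5 singles out as of most interest, and the Protocol (Activity 4, number of subjects) expects enrolment above the minimum to allow subgroup examination.

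**Working it through.** **Step 1: follow the coding.** Missing race goes to *Other/Unknown* (section 4.6). That level is not White/Non-Hispanic (Table 8). Item 5 has only one other level, *Others* (section 4.5). With no further rule, the patient lands in *Others*.

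**Step 2: is any race missing?** After its list of five covariates (race/ethnicity, employment, insurance, rurality, socio-economic status), section 4.6 notes that a preliminary check found no missing values in the remaining covariates. The natural reading is that race has some. No count is given.

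**Step 3: is race alone in this?** Among the seven subgroups, cohort and region are fixed by design. By the same note, age, sex and cancer type are complete. Missing rurality is excluded. Race is the only subgroup where an unknown value is placed in a substantive level.

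**Step 4: size.** The plan states no figure to reproduce. Both inputs below are assumptions:

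- *m*: fraction of all patients with missing race
- *π*: White/Non-Hispanic share among patients with known race; the unknowns are given the same mix

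It is also assumed that the effect in an unknown-race patient depends only on true race. Then:

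- Size of *Others*: P = (1 − m)(1 − π) + m
- Share of *Others* with unknown race: u = m / P
- Share of the true contrast retained: r = 1 − uπ, which simplifies to (1 − π) / P

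Worked case, π = 0.80 and m = 0.05: P = 0.95 × 0.20 + 0.05 = 0.24; u = 0.05 / 0.24 = 20.8%; r = 0.20 / 0.24 = 0.83, a shrinkage of 17%.

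| π | m | P | Unknown share of *Others* | Retained r | Shrinkage |
|---|---|---|---|---|---|
| 80% | 1% | 0.208 | 4.8% | 0.96 | 4% |
| 80% | 2% | 0.216 | 9.3% | 0.93 | 7% |
| 80% | 5% | 0.240 | 20.8% | 0.83 | 17% |
| 80% | 10% | 0.280 | 35.7% | 0.71 | 29% |
| 90% | 1% | 0.109 | 9.2% | 0.92 | 8% |
| 90% | 2% | 0.118 | 16.9% | 0.85 | 15% |
| 90% | 5% | 0.145 | 34.5% | 0.69 | 31% |
| 90% | 10% | 0.190 | 52.6% | 0.53 | 47% |

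The result is sensitive to who the unknowns are. At m = 5%, if only half of them are White and non-Hispanic, the retained share rises to 1 − 0.208 × 0.5 = 0.90 (π = 80%) or 1 − 0.345 × 0.5 = 0.83 (π = 90%). If none are, there is no dilution.

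**Step 5: net effect on detection.** Removing the unknowns also makes the comparison group smaller. With equal outcome variance and equal exposure balance across groups, the standard error of the contrast is proportional to √(1/p_Others + 1/p_White). For π = 0.80, m = 0.05:

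- Recorded race only: 1/0.19 + 1/0.76 = 6.58
- Unknowns pooled: 1/0.24 + 1/0.76 = 5.48
- Ratio of z-statistics, pooled to recorded: 0.833 × √(6.58 / 5.48) = 0.91

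The loss in the z-statistic is about 9%, against a 17% shrinkage of the estimate. For π = 0.90, m = 0.05, the sums are 1/0.095 + 1/0.855 = 11.70 and 1/0.145 + 1/0.855 = 8.07. The ratio is 0.690 × √(11.70 / 8.07) = 0.83, a loss of about 17% against a 31% shrinkage.

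**The case against.** The strongest reply is that this is an unspecified detail, not a documented miscoding. The missing-covariate rules are introduced for the primary analysis, section 4.5 gives no missing-data rule of its own, and its level is called *Others*, not *Other/Unknown*. A programmer who built item 5 from recorded race only would not contradict section 4.5. That is fair, and it is why the point is limited to the plan as written. But no other rule is offered, so a programmer following the SAP literally would pool the unknowns.

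A reader might infer that the unknowns are mostly White and that the contrast is therefore badly blurred. The documents do not support this. They give no racial make-up for the sites, for the patients or for those with missing race, and no count of missing values. At around 1% missing, the effect is small.

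A reader might also infer that the chance of finding a difference falls by the shrinkage percentage, or that a lack of benefit in minority patients would be missed because of this coding. Step 5 shows that the first overstates the loss. As for the second, the SAP already says power is insufficient in subgroups, so a difference could be missed under either coding, and no decision rule depends on item 5.

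Finally, excluding unknowns is a complete-case choice with its own selection risk if race is not missing at random. That stands, and it favours showing the unknowns as a separate row over simply dropping them.

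**Conclusion.** The point holds as a low-priority improvement. Read together, sections 4.4 to 4.6 place patients of unknown race in a substantive subgroup, and no known-race or imputed version of that subgroup is planned. The size cannot be determined from the documents. Under the stated assumptions (80–90% White and non-Hispanic among known patients, unknowns of the same mix, effect depending only on true race), shrinkage is about 4–8% at 1% missing and 17–31% at 5% missing. If few unknowns are White and non-Hispanic, it is close to nil. If the effect in unknown-race patients differs for other reasons, the direction is not assured, but the *Others* row would still not describe patients of recorded minority race.

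The consequence is confined to one exploratory contrast. The primary effect estimate uses the four-level covariate, not this two-level split, and a reader should not infer any problem with the primary result.

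**What to change.** In SAP section 4.5, item 5, define the contrast as White/Non-Hispanic against recorded Black, Hispanic or other race or ethnicity. Show patients with missing race as a separate row, or leave them out of this contrast in line with the exclusion already used for missing rurality. In either case report how many there are, by eSyM condition. Keep *Other/Unknown* as a covariate level in the main model, so the primary analysis does not change.

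The cost is one line of text, a somewhat smaller comparison group, and a complete-case assumption for this exploratory contrast. When the variable is derived, missing race must be kept apart from a recorded race of *other*, which the current combined level does not do.

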4.6. Sensitivity analyses

Change in eSyM recall period:

During the study, there was a minor update to the eSyM symptom questionnaire. eSyM originally collected symptom information with a 7-day recall period, but a mid-study update altered this to a 24-hour recall period. Using eSyM+ data only, we will summarize frequencies of severe symptoms reported before the update and after the update. For the evaluation of eSyM intervention, we will not distinguish eSyM intervention before and after the update in the primary analysis. As sensitivity analyses, we will assess the impact of this update on each outcome.

- Sensitivity Analysis 1: We will run the same analysis as the primary analysis, excluding the eSyM+ episodes with a 7-day recall period.
- Sensitivity Analysis 2: We will modify the GLMM model used for the primary analysis. The intervention group variable will be a categorical variable with three levels – control, eSyM+ with 7-day recall, and eSyM+ with 24-hour recall. We will test if there is any difference between the 7-day and 24-hour recall.

Missing data:

Given the short 30-day interval for the Aim 2a primary endpoint and our pragmatic outcome, we expect the dropout fraction and missing data at Day 30 to be negligible. Subjects with no hospital encounters by Day 30 will be included in the analysis as having had no EDTR.

Regarding missing covariates, the primary analysis will be based on the following data handling.

- 1) Race/Ethnicity: Subjects with missing race/ethnicity are categorized as “Other/Unknown” and included in the analysis.
- 2) Employment: Subjects with missing employment information are categorized as “Other/Unknown” and included in the analysis.
- 3) Insurance type: Subjects with missing insurance type are categorized as “Other/Unknown” and included in the analysis.
- 4) Rurality: Subjects with missing rurality will be excluded from the analysis.
- 5) Socio-economic status: Subjects with missing socio-economic status are classified as “poverty level 2” and included in the analysis.

Note that the preliminary data check found that the other covariates do not have missing values.

In secondary analysis, we will perform multiple imputations with chained equations for Rurality. Specifically, the imputation models will include the primary outcome (EDTR Day 30), all variables used for the primary analysis (Category A and B), and the variables in C (as auxiliary variables) listed in Table 8. The number of complete datasets we generate will basically the same as the percentage of the fraction of missing. For example, if the missing fraction is 10%, we will generate 10 complete datasets. However, if the fraction of missing is less than 5%, we will generate 5 complete datasets. We will analyze each complete data and obtain the point estimate and the standard error for the intervention effects. We will then pool the results from the multiple complete datasets using Rubin’s method.¹³

Analysis with data from the first episode:

In the primary analysis, all episodes in the analyses except for eSyM- episodes contaminated with the eSyM intervention will be included. We will perform sensitivity analyses using only the first episode from each patient. In these sensitivity analyses, each patient will serve only one data point in the analysis.

Modeling for the COVID19

As a sensitivity analysis, we will include the site-specific COVID19 prevalence as a time-varying covariate in the model.

4.7. Power Considerations

We estimate a minimum of 6048 patients will be enrolled. (see Section 3.3 for details). Since some subjects may experience more than one trigger event (see Section 4.2 General Analysis Approach: *Multiple episodes for medical record data*), the study participants will potentially contribute multiple data points. The goal of the power calculation for this study is to confirm that the study has sufficient power to assess the effects of the intervention on the outcomes. Therefore, for the power calculations throughout this SAP, we will conservatively estimate the power, assuming that an individual patient provides only one episode.

The probability that a patient who has a trigger event experiences EDTR within 30 days after the trigger event is estimated to vary between 8% to 15% for the control group, based on the HCUP data, institutional data, and early phase analyses from CMMI's Oncology Care Model for Baptist Memorial, the only Oncology Care Model participant among our 6 sites. We hypothesize that the probability of experiencing EDTR by Day 30 will be 3 to 4% lower in the eSyM+ group.

Table 9 shows the required sample sizes for the study to have 80% power to detect the difference between groups, at two-sided alpha level 0.05, using the SW-RCT design.¹⁴ Analyses of inter-institutional variation in hospitalization rates and ED visit rates from AHRQ's statewide databases indicate that low ICC estimates are appropriate.^{15,16} Furthermore, we expect a low ICC because: 1) the intervention will be deployed using the same technology across sites; 2) we will adjust for variation in baseline risk via GLMMs such that any potential differences in case-mix among sites will be negligible. Given these factors, the conservative estimate of 6048 participants provides adequate power to address the Aim 2a primary outcome.

Note that we used the sample size formula¹⁴ that assumes exchangeable correlations because we originally had planned to include sites as random effects. However, since the number of sites is only 6 in this study, we modified the analysis plan and decided to include sites as fixed effects in the primary analysis. We acknowledge that our original sample size calculation (above) may not be precise due to this, but it should still work as a conservative estimate.

Table 9. Required total sample size with various scenarios for 80% power					
The probability of experiencing EDTR by Day 30		Effect size		N required	
Control (eSyM-)	Intervention (eSyM+)	Absolute	Relative	Low ICC (0.01)	Moderate ICC (0.05)
8%	5%	3%	38%	2192	5844
9%	6%	3%	33%	4485	6816
10%	7%	3%	30%	5047	7721
11%	8%	3%	27%	5598	8606
12%	8%	4%	33%	3246	4810
13%	9%	4%	31%	3538	5283
14%	10%	4%	29%	3823	5746
15%	11%	4%	27%	4103	6198

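### SAP 4.7 claims adequate power at 6,048 without limit, but a 3-point EDTR reduction at control risks of 13-15%, inside its own stated range, falls short of 80%

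*SAP*

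**What the plan says.** SAP section 4.7 (Power Considerations) gives two ranges. The control risk "is estimated to vary between 8% to 15% for the control group". For the effect: "We hypothesize that the probability of experiencing EDTR by Day 30 will be 3 to 4% lower in the eSyM+ group". No sentence assigns the smaller reduction to low control risks or the larger one to high control risks.

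The text then introduces the table: "Table 9 shows the required sample sizes for the study to have 80% power to detect the difference between groups". The significance level is 5%, two-sided. Table 9 has eight rows. The 3-point rows stop at 11% versus 8% ("11% 8% 3% 27% 5598 8606"). The 4-point rows run from 12% versus 8% to 15% versus 11% ("15% 11% 4% 27% 4103 6198"). The last two numbers in each row are the required totals under the low and moderate ICC headings. No row shows 3 points at 12-15%.

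After arguing that a low ICC is appropriate, the SAP concludes that "the conservative estimate of 6048 participants provides adequate power to address the Aim 2a primary outcome". That sentence names no control risk, effect size or ICC.

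**The concern.** Read as written, the inputs allow any reduction from 3 to 4 points at any control risk from 8% to 15%. In the low-ICC column the required total climbs to 5,598 at 11% versus 8%, then drops to 3,246 at 12% versus 8% because the effect changes from 3 to 4 points. The part of the input range that needs the most patients, the smaller effect at the higher control risks, is not tabulated, yet the adequacy sentence covers it.

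The trial does not choose the control risk. If it turns out at 13-15% and eSyM achieves the lower end of the hypothesised effect, the stated minimum size has less than the 80% power a reader would assume. A null primary result could then be read against a power statement that was never shown for that scenario.

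**Working it through.** **Inputs.** Two-sided alpha 0.05, 80% power, N = 6,048 and one episode per patient (SAP 4.7); 6 sites, 6 steps and 7 periods including the run-in (SAP 3.1); equal cluster sizes (SAP 3.3). Cluster-period size is m = 6,048 / (6 × 7) = 144.

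**Formulae.** The exchangeable-correlation stepped-wedge calculation, with sites random:

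- Unadjusted n per arm = [1.96 √(2 p̄(1−p̄)) + 0.842 √(p1(1−p1) + p2(1−p2))]² / (p1−p2)²
- Design effect on the total, with k = 6: DE = [1 + ρ(km + m − 1)] / [1 + ρ(km/2 + m − 1)] × 3(1−ρ) / [2(k − 1/k)] × 7
- Required total = 2n × DE, solved iteratively because m depends on the total
- Power at 6,048: put 6,048 / (2 DE) per arm into the two-proportion formula

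**Reproducing Table 9, low-ICC column.**

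| Control v eSyM | Printed | ICC 0.0001 | ICC 0.01 |
|---|---|---|---|
| 8% v 5% | 2,192 | 3,914 | 6,198 |
| 9% v 6% | 4,485 | 4,485 | 7,128 |
| 10% v 7% | 5,047 | 5,047 | 8,039 |
| 11% v 8% | 5,598 | 5,598 | 8,928 |
| 12% v 8% | 3,246 | 3,246 | 5,101 |
| 13% v 9% | 3,538 | 3,538 | 5,581 |
| 14% v 10% | 3,823 | 3,823 | 6,049 |
| 15% v 11% | 4,103 | 4,103 | 6,505 |

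Rows 2-8 match at ICC 0.0001, not at the printed 0.01. (The value 0.01%, which is 0.0001, is the lowest ICC in Table 11.) Row 1 matches neither.

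**Design effect at 6,048.**

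- ICC 0: 3 / [2 × (6 − 1/6)] × 7 = 1.800, or 1,680 effective patients per arm
- ICC 0.0001: (1.1007 / 1.0575) × 0.9999 × 1.8 = 1.873, or 1,614 per arm
- ICC 0.01: (11.07 / 6.75) × 0.99 × 1.8 = 2.922, or 1,035 per arm

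**The missing rows: a 3-point reduction.** Example, 15% v 12% at ICC 0.0001: z = [0.03 × √1,614 − 1.96 × √(2 × 0.135 × 0.865)] / √(0.1275 + 0.1056) = (1.205 − 0.947) / 0.483 = 0.535, so power is 70.4%.

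| Control v eSyM | Power, ICC 0 | Power, ICC 0.0001 | Power, ICC 0.01 | N for 80%, ICC 0.0001 |
|---|---|---|---|---|
| 12% v 9% | 81.0% | 79.4% | 60.5% | 6,140 |
| 13% v 10% | 77.8% | 76.2% | 57.1% | 6,672 |
| 14% v 11% | 74.9% | 73.2% | 54.1% | 7,193 |
| 15% v 12% | 72.1% | 70.4% | 51.5% | 7,703 |

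A direct stepped-wedge variance calculation agrees to about 0.1 point (79.5% at 12% v 9%, ICC 0.0001).

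**The tabulated 3-point rows at the printed ICC.** At ICC 0.01 the same formula gives 79%, 74%, 69% and 64% at control risks of 8%, 9%, 10% and 11%. At ICC 0.0001 it gives 93%, 90%, 86% and 83%.

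**The case against.** **A pairing may have been intended.** Table 9's relative effects all lie between 27% and 38%. Three points at 12%, 13%, 14% and 15% would be 25%, 23%, 21% and 20%, below anything tabulated. That is an ordinary reason to move to 4 points, and it makes a pairing plausible. But the text does not state it, and the adequacy sentence is not confined to the tabulated pairs. This objection shapes the remedy; it does not remove the point.

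**6,048 is a floor.** SAP 3.3 calls it conservative and sets no cap, SAP 3.6 adds a period, and the protocol's Activity 5 reports data on more than 13,000 patients. At 13,000 with equal allocation, 15% versus 12% would have about 95% power at ICC 0.0001 and 82% at 0.01. This stands against inferring that the completed trial is underpowered. It does not support a sentence about 6,048.

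**Stronger readings to resist.** A reader might infer that the table changes effect size at 12% because 3 points stops fitting there. The documents do not support that: 12% versus 9% needs 5,897 at ICC 0, which fits, and 6,140 at ICC 0.0001, a 1.5% excess. No motive should be drawn. A reader might also infer that 6,048 is secure for 3 points up to 11-12%. That is true only at an ICC of about 0.0001, which Table 9 does not print.

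**Conclusion.** The point holds for control risks of 13-15%. Over the SAP's own unpaired inputs, the unrestricted adequacy claim is not delivered for a 3-point reduction there. The shortfall from 80% is about 2, 5 and 8 points at ICC 0, about 4, 7 and 10 points at ICC 0.0001, and 23 to 28 points at the printed 0.01. At ICC 0.0001 the smallest reduction detectable with 80% power is about 3.13, 3.24 and 3.35 points, so on that assumption the gap is modest. At 12% the case is borderline and should not be counted.

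These figures assume random sites, equal cells and seven periods, as in the SAP's cited formula. The primary model now has fixed sites. A linear approximation with fixed site-by-cohort effects and categorical periods gives about 54%, 51% and 49%, so that change does not rescue the claim. The primary model uses a spline for time, so its exact figures will differ.

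This is a defect in the power statement, not evidence that the trial is too small.

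**What to change.** In SAP 4.7, restrict the adequacy sentence in one of two ways:

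1. If the pairing was intended, state that 3 points applies to control risks of 8-11% and 4 points to 12-15%, and limit the claim to those pairs.
2. Otherwise, add the 3-point rows for 12%, 13%, 14% and 15% to Table 9, and state that 6,048 does not reach 80% power for 3 points at 13-15%.

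Either way, label each restated figure with the ICC and the model actually used. Do not write that 6,048 gives 80% power for 3 points up to 11-12% unless ICC 0.0001 is named. The label matters for the pairing option too: at the printed 0.01 none of the four 3-point rows reaches 80%, and 15% versus 11% gives about 77%. The 8% versus 5% low-ICC entry should be rechecked when the table is reissued.

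The cost is a sentence or two and at most four table rows, with a less favourable stated power for part of the range. No extra enrolment or design change is needed.
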